4.4 SAFETY ASSESSMENTS

4.4.1 Adverse Events

AEs will be collected starting after the subject has signed the informed consent and completed any study assessment until the end of the final study visit. The date of onset, date ended, severity, relationship to study drug, therapy required, and action taken regarding study drug and study participation will be reported for each AE.

See Section 6 for additional information regarding the evaluation of adverse events.

4.4.2 Physical Exam

A brief physical exam will be performed at Screening, Baseline (Day 0) and Week 12/ET. If clinically significant changes in the physical examination from Baseline are noted at the Week 12/ET visit, these will be recorded as adverse events.

4.4.3 Vital Signs

Blood pressure and pulse rate will be collected at Screening, Baseline, and at Weeks 2, 4, 8, and 12/ET. Any clinically significant changes in vital signs from Baseline will be recorded as adverse events whether or not drug related.

4.4.4 Pregnancy Testing

All WOCBP must have a UPT at Screening and Baseline and if the result is positive, the subject will not be allowed to participate in the study. Refer to Section 6.4 for further information.

A female is considered to be of childbearing potential UNLESS she is post-menopausal (no menses for 24 consecutive months), surgically sterilized, or without a uterus and/or both ovaries. Premenarchal subjects will be considered to be of childbearing potential for this study.

Pregnancy tests will also be performed at Weeks 4, 8, and 12/ET. If a subject is determined to be pregnant prior to Week 12, the subject will be discontinued from the study but followed until term.

4.5 ADDITIONAL ASSESSMENTS

4.5.1 Photography

Photographs of the face will be taken at Baseline and Weeks 4, 8, and 12/ET at a subset of sites. Baseline photographs may be reviewed by the sponsor or members of the study team to confirm appropriateness of enrolled subjects.

4.6 SCREEN FAILURES

A subject is considered screened once they have signed the ICF and completed one screening assessment. A screen failure subject will be any screened subject who does not meet the study eligibility requirements. Subjects will not be allowed to rescreen. Screen failures will not be recorded in the case report form (CRF).

4.7 PROTOCOL DEVIATIONS

This study will be conducted as described in this protocol, except for an emergency situation in which the protection, safety, and well-being of the subject requires immediate intervention, based on the judgment of the Investigator (or a responsible, appropriately trained professional designated by the Investigator). In the event of a significant deviation from the protocol due to an emergency, accident, or mistake, the Investigator or designee must contact Chiltern at the earliest possible time

by telephone. This will allow an early joint decision regarding the subject's continuation in the study. This decision will be documented by the Investigator and Chiltern.

5. PROHIBITED THERAPIES AND MEDICATIONS

Concomitant medications are any prescription or over-the-counter (OTC) preparations. Use of concomitant medications will be recorded on the concomitant medications study record and study database beginning at the Baseline Visit until the final evaluation (Week 12/ET).

Subjects will be permitted to apply non-comedogenic moisturizer or sunscreen on an as-needed basis. Moisturizer must not contain antibacterials and the subject should not change moisturizer and/or sunscreen used during the course of the study. If used, moisturizers and sunscreen should be applied at least 30 minutes after study drug application.

Subjects must not have used anti-acne treatments including topical agents to the face, systemic antibiotics or procedures that may impact acne (as described in Section 3.7.3) prior to Baseline. These medications and procedures are also prohibited during the trial. Topical anti-acne agents may be used to treat acne on the chest, back or upper shoulders in this study.

Subjects may not be concurrently on drugs associated with exacerbating acne vulgaris. (Appendix 16.1). Subjects who have used an investigational drug or device within 30 days of Baseline should not be enrolled. Subjects must not participate in a different interventional research study during the study period. Any subject who has participated in a previous study with SB204 or NVN1000 Gel must not participate.

Any medication/therapy used by the subject following first application of study product will be considered a concomitant medication (e.g., aspirin, acetaminophen, birth control pills, vitamins, etc.). Every attempt should be made to keep concomitant medication/therapy dosing constant during the study. Any change to concomitant medications/therapies should be noted on the subject's study record and in the study database. When applicable, an AE should be completed for any subject starting a concomitant medication/therapy after enrollment into the study.

6. EVALUATION OF ADVERSE EVENTS

6.1 DEFINITIONS

An adverse event (AE) is any untoward medical occurrence (e.g., sign, symptom, disease, syndrome, intercurrent illness, clinically significant abnormal laboratory finding, injury or accident) whether or not considered drug related. Any AE that emerges or worsens following administration of the informed consent and until the end of study participation will be collected. A pre-existing condition is one that is present prior to the start of the study and is to be reported as part of the subject's medical history. It should be reported as an AE only if the frequency, intensity, or the character of the condition worsens during the study.

An adverse event or suspected adverse reaction is considered “unexpected” if it is not listed in the Investigator’s Brochure or is not listed at the specificity or severity that has been observed.

A serious adverse event (SAE) includes any event, if in the view of either the Investigator or Medical Monitor results in any of the following outcomes:

- Death
- Life-threatening event (i.e., the subject was, in the opinion of the Investigator, at immediate risk of death from the event as it occurred. It does not apply to an AE that hypothetically might have caused death if it were more severe.)
- Persistent or significant disability/incapacity (i.e., the AE results in a substantial disruption of the subject’s ability to carry out normal life functions)
- Requires in-patient hospitalization or prolongs hospitalization (i.e., the AE required at least a 24-hour in-patient hospitalization or prolonged a hospitalization beyond the expected length of stay; hospitalizations for elective medical/surgical procedures, scheduled treatments, or routine check-ups are not SAEs by this criterion)
- Congenital anomaly/birth defect (i.e., an adverse outcome in a child or fetus of a subject exposed to the molecule or investigational product before conception or during pregnancy)
- Does not meet any of the above serious criteria but may jeopardize the subject or may require medical or surgical intervention to prevent one of the outcomes listed above (i.e., is a significant or important medical event)

6.1.1 Adverse Event Severity Grades

The Investigator is responsible for evaluating all AEs and determining the severity of the event. Severity will be categorized according to the following definitions:

- Mild: Event may be noticeable to subject; does not influence daily activities; usually does not require intervention
- Moderate: Event may be of sufficient severity to make subject uncomfortable; performance of daily activities may be influenced; intervention may be needed
- Severe: Event may cause severe discomfort; usually interferes with daily activities; subject may not be able to continue in the study; treatment or other intervention usually needed.

The Investigator will follow all subjects who experience AEs until there is a return to the subject’s Baseline condition or until a clinically satisfactory resolution is achieved or the subject is lost to follow-up.

6.1.2 Investigational Product Causality

Relationship of an AE to investigational product will be assessed as follows:

- **Definite:** There is a clinically plausible time sequence between the onset of the AE and the application of investigational product; when the event responds to withdrawal of investigational product and recurs with re-administration of investigational product.
- **Probable:** There is a clinically plausible time sequence between the onset of the AE and the application of investigational product; the AE is unlikely to be caused by the concurrent/underlying illness, other drugs or procedures.
- **Possible:** There may or may not be a clinically plausible time sequence between the onset of the AE and the application of investigational product and a cause cannot be ruled out.
- **Unlikely:** There is no reasonable temporal association between the test material and the suspected event and the event could have been produced by the subject's clinical state or other modes of therapy administered to the Subject.
- **Unrelated:** This term should be reserved for those events that cannot be even remotely related to study participation.

6.2 REPORTING ADVERSE EVENTS

For the purpose of AE reporting the trial period is defined as the period after the subject signs the informed consent/assent and completed one study assessment to the end of subject's last visit.

The Investigator will assess subjects at each scheduled study visit for the occurrence of AEs. In order to avoid bias in eliciting AEs, subjects should be asked the following non-leading question: "*How have you felt since your last visit?*" All AEs (serious and non-serious) reported by the subject must be recorded on the subject's study record and entered into the study database.

In addition, Chiltern must be notified within 24 hours of the Investigator's knowledge of the event by telephone or email of any immediately reportable events according to the procedure outlined below. Special attention should be paid to recording hospitalizations and concomitant therapies and medications.

6.3 IMMEDIATELY REPORTABLE EVENTS

Serious adverse events (SAEs) are considered immediately reportable events. Any SAE, whether deemed drug-related or not, must be reported to Chiltern by telephone, email, or fax as soon as possible after the Investigator or coordinator has become aware of its occurrence. The Investigator/coordinator must complete a Serious Adverse Event (SAE) Form and fax/email it to Chiltern within 24 hours of notification of the event. When appropriate, Novan will notify the appropriate regulatory body of drug related Serious Adverse Events.

Serious Adverse Event (SAE) and Safety Contact Information:

Phone: SAE Hotline: [name]

Email: [contact]

[contact]

If a subject experiences an SAE or pregnancy the Investigator must:

1. Report the SAE or pregnancy by telephone, fax, or email immediately (within 24 hours) after the Investigator becomes aware of the event.
2. Complete an SAE or Pregnancy Notification Form and fax/email or overnight courier to Chiltern within 24 hours of knowledge of the event.
3. Obtain and maintain all pertinent medical records, information and medical judgments of medical personnel who assisted in subject's treatment and follow-up and document as appropriate.
4. Provide a more detailed report to both Chiltern and the IRB, if applicable, no later than seven days after the Investigator discovers the event as further information becomes available, and when necessary update the information with follow-up information including outcomes. This report should include a statement as to whether the event was or was not related to the use of investigational product.
5. The Investigator will notify the IRB of the SAE or pregnancy according to specific IRB requirements.
6. The Investigator will collect information on SAEs until the subject's health has returned to Baseline status, until all parameters have returned to normal, or remaining health issues have otherwise been explained.

6.4 PREGNANCY

Women of child-bearing potential (WOCBP) must use an effective method of birth control during the course of the study and for 30 days following their final study visit. Allowable methods of birth control include stabilized on oral contraceptive for at least three months, IUD, condom with spermicide, diaphragm with spermicide, implant, NuvaRing®, injection, transdermal patch or abstinence with a documented second acceptable method of birth control should the subject become sexually active. Females taking hormonal contraceptives must have taken the same type for at least three months (90 days) prior to entering the study and must not change type during the study. Those who have used birth control pills or hormonal contraception in the past and stopped must have discontinued usage at least three months prior to the start of the study.

A female is considered to be of childbearing potential unless she is post-menopausal (no menses for 24 consecutive months), surgically sterilized, or without a uterus and/or both ovaries.

Before enrolling any subject in this clinical trial, the Investigator must review guidelines about study participation including the topics below:

- Informed consent document
- Pregnancy prevention information
- Risks to unborn child(ren)

- Any drug interactions with hormonal contraceptives
- Contraceptives in current use
- Guidelines for the follow-up of a reported pregnancy

Prior to study enrollment, all subjects must be advised of the importance of avoiding pregnancy during participation in this clinical study and the potential risk factors for an unintentional pregnancy. The subject must sign an informed consent document stating that the above-mentioned risk factors and the consequences were discussed.

During the study, WOCBP should be instructed to contact the Investigator immediately if they suspect they might be pregnant (e.g., missed or late menstrual cycle). The Investigator must immediately notify Chiltern of any female subject who becomes pregnant any time during study participation, record the information on the Pregnancy Notification Form and email the form to Chiltern. Subjects found to be pregnant prior to Week 12 will be discontinued from the study. Chiltern will ask the site to follow-up with the subject periodically during the pregnancy for ongoing health and safety information through term, as applicable. Protocol-required procedures for the Week 12/ET evaluation must be performed for the subject.

6.5 FOLLOW-UP OF ADVERSE EVENTS

6.5.1 Follow-Up of Non-Serious Adverse Events

Non-serious AEs that are not resolved at the time of the last scheduled study visit (Week 12/ET) must be recorded in the study database as ongoing/not recovered/not resolved.

6.5.2 Follow-Up of Post Study Serious Adverse Events

Serious adverse events that are identified on the last scheduled contact (Week 12/ET) must be recorded in the study database and reported to Chiltern according to the reporting procedures outlined in Sections 6.2 and 6.3. This may include unresolved previously reported SAEs, or new SAEs. The Investigator should follow these SAEs until the events are resolved, or the subject is lost to follow-up. The Investigator should continue to report any significant follow-up information to Chiltern and the IRB up to the point the event has been resolved. Resolution means the subject has returned to the Baseline state of health, or the Investigator does not expect any further improvement or worsening of the subject's condition.

Any new SAEs reported by the subject to the Investigator that occur after the last scheduled contact and are determined by the Investigator to be reasonably associated with the application of investigational product should be reported to Chiltern and the IRB.

6.6 OVERDOSAGE

There is no specific antidote for nitric oxide. In the event of an overdose, best supportive care should be utilized. Methylene blue may be used to treat subjects exhibiting methemoglobinemia.

6.7 DISCONTINUATION OF INDIVIDUAL SUBJECTS FROM THE STUDY

Subjects who develop intolerance to the product as defined by scores of 3 (severe) on 2 or more categories of tolerability (erythema, scaling, dryness, pruritus, burning/stinging) shall be discontinued from the study.

If a subject is determined to be pregnant prior to Week 12, the subject will be discontinued from the study but followed until term.

7. STATISTICAL ANALYSIS

7.1 GENERAL CONSIDERATIONS

All statistical processing will be performed using SAS® unless otherwise stated. Statistical significance will be based on two-tailed tests of the null hypothesis resulting in p-values of ≤ 0.05 unless stated otherwise.

Continuous data will be summarized with sample size (N), mean, median, standard deviation, minimum and maximum. Categorical data will be summarized with N, frequency counts, and percentages, based on N. Data will be presented for the active treatment group and vehicle treatment group. Demographic and Baseline data will also be presented over both treatment groups.

A detailed description of the statistical methodology and data reporting for this study will be provided in the Statistical Analysis Plan (SAP). The SAP will be finalized before the database is locked and released to Novan. Any deviations from the SAP will be justified in the clinical study report.

7.2 POPULATIONS

7.2.1 Intent to Treat (ITT) Population

The intent to treat (ITT) population will include all study subjects who were randomized and dispensed study medication and grouped by the treatment to which they were assigned at randomization. All efficacy analyses will be performed on the ITT population.

7.2.2 Safety Population

The safety (SAF) population will include all randomized subjects who received at least one dose of study medication. All safety and tolerability analyses will be performed on the safety analysis population (SAF) population based on the treatments the subjects actually applied.

7.2.3 Per-Protocol Population

The per protocol (PP) population will include subjects who complete the Week 12 evaluation without noteworthy study protocol violations (i.e., any subject or investigator activity that could have possibly interfered with the therapeutic administration of the treatment or the precise

evaluation of treatment efficacy). The PP population will include subjects in the SAF population who do not meet any of the following criteria:

- Violated the inclusion/exclusion criteria;
- Have taken any interfering concomitant medications;
- Did not attend the Week 12 visit;
- Have not been compliant with the dosing regimen;
- Out of visit window at the Week 12 visit by ± 7 days.

Prior to breaking the blind, other additional criteria may be added to the list to accommodate for unforeseen events that occurred during the conduct of the trial that result in noteworthy study protocol violations. To determine dosing non-compliance criteria, the data will be reviewed in a blinded manner and a cut-point will be determined.

7.3 DEMOGRAPHIC AND BASELINE CHARACTERISTICS

Subject demographic and Baseline characteristics will be summarized by treatment group and overall for the ITT, PP and SAF populations. For continuous variables (e.g., age), mean, median, standard deviation, minimum and maximum will be presented. Categorical variables (e.g., ethnicity, race) will be summarized with frequency count and percentage by treatment group. Age will also be categorized and summarized as proportion of adults ($\text{age} \geq 18$) and juvenile ($\text{age} < 18$).

7.4 EFFICACY ANALYSIS

Efficacy of SB204 4% will be based on statistical superiority over vehicle for change from Baseline in lesion counts and improvement in IGA score at Week 12/ET.

7.4.1 Primary Efficacy Analyses

There are three co-primary efficacy outcomes:

- change in inflammatory lesions counts at Week 12/ET
- change in non-inflammatory lesions counts at Week 12/ET and
- IGA success at Week 12/ET which is defined as an IGA score of clear (0) or almost clear (1) and ≥ 2 grades less than Baseline

All three co-primary outcomes must show superiority over vehicle ($p\text{-value} \leq 0.05$) in order for efficacy to be demonstrated; therefore no multiplicity adjustments will be made to the co-primary outcome analyses..

Prior to analysis of co-primary outcomes, missing post-Baseline lesion counts and IGA scores results at each visit will be imputed using a Markov chain Monte Carlo (MCMC) multiple imputation methodology. Separate multiple imputation (MI) procedures will be used for each outcome, using Statistical Analysis Software (SAS) procedure MI. Details of PROC MI and options used in the imputation procedures will be provided in a statistical analysis plan. ITT

subjects with only Baseline assessments will have the Baseline value carried forward across all visits.

The primary analyses of the co-primary efficacy endpoints will be performed in the ITT population where missing data have been imputed as described above. Additional analyses of the co-primary outcomes will be performed using the PP population. To assess the sensitivity of the primary efficacy results to imputation methods, each co-primary outcome will be analyzed as described above, but with missing data imputed by last observation carried forward (LOCF) and Baseline observation carried forward (BOCF) on the ITT population.

7.4.2 Secondary Efficacy Analyses

Secondary efficacy outcomes include the percent change in inflammatory and non-inflammatory lesion counts at Week 12/ET, the median time to 35% improvement in inflammatory lesions and the time to a two or more grade improvement in the IGA.

Analysis of the secondary efficacy outcomes will be adjusted for multiplicity using a hierarchical step-down procedure. These endpoints will be tested in the specified order with the rule that once a p-value exceeds 0.05, endpoints further down in the order are not statistically significant. The order will be as follows:

- 1) Percent change in inflammatory lesions at Week 12/ET
- 2) Percent change in non-inflammatory lesions at Week 12/ET
- 3) Median time to achieve 35% reduction in inflammatory lesions
- 4) Median time to a two or more grade improvement in the IGA.

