All three co-primary outcomes must show superiority over vehicle (p-value \leq 0.05) in order for efficacy to be demonstrated; therefore no adjustments for multiplicity will be made.

Secondary Efficacy Analyses

Secondary efficacy outcomes include the percent change in inflammatory and non-inflammatory lesion counts at Week 12/ET, the median time to 35% improvement in inflammatory lesions, and the median time to a two or more grade improvement in IGA.

Analysis of the secondary efficacy outcomes will be adjusted for multiplicity using a hierarchical step-down procedure. These endpoints will be tested in the specified order with the rule that once a p-value exceeds 0.05, endpoints further down in the order are not statistically significant.

Tolerability Analyses

Cutaneous tolerability assessments (erythema, scaling, dryness, pruritus, burning/stinging) will be summarized from Baseline to Week 12/ET. Additionally, change from Baseline in tolerability assessments will be summarized at Weeks 2, 4, 8, and 12/ET.

Safety Analyses

Adverse Events

All AEs that occur during the study will be recorded and classified on the basis of Medical Dictionary for Regulatory Activities (MedDRA) terminology. Treatment-emergent AEs (TEAEs) are defined as AEs with an onset on or after the date of the first study drug dose. Adverse events noted prior to the first study drug administration that worsen after Baseline will also be reported as AEs and included in the summaries.

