3.1 STUDY ENDPOINTS

3.1.1 Efficacy Endpoints

Primary Efficacy Endpoints

The co-primary efficacy endpoints are:

- The absolute change in inflammatory lesion count from Baseline to Week 12/ET;
- The absolute change in non-inflammatory lesion count from Baseline to Week 12/ET;
- The proportion of subjects with IGA success at Week 12/ET. A subject will be considered a success if the IGA score is clear (0) or almost clear (1) and ≥ 2 grades less than Baseline

Secondary Efficacy Endpoints

The secondary efficacy endpoints include the following:

- The percent change in inflammatory lesion count from Baseline to Week 12/ET;
- The percent change in non-inflammatory lesion count from Baseline to Week 12/ET;
- The median time to a 35% reduction in inflammatory lesion counts;
- The median time to a two (2) or more grade improvement in IGA.

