7.8 SAMPLE SIZE AND POWER CONSIDERATIONS

Approximately 1300 subjects will be randomized into the study in a 1:1 ratio (650 in each arm) at approximately 50 sites in North America. In the previous phase 2 study, the pooled vehicle IGA ‘success’ rate was 7.1% and the pooled SB204 IGA success rate was 13.4%. Using NQuery Advisor v7 (Statistical Solutions, Ltd) to estimate sample size and statistical power, based on a vehicle IGA success rate of 7% and a 6% difference for the SB204 arm, a sample size of 1294 was estimated to have at least 95% power for a two-sided test at the $\alpha=0.05$ level using the continuity corrected chi-square test.

The statistical power for detecting treatment differences in inflammatory or non-inflammatory lesions exceeds 99% once at least 256 subjects are treated in each group. This is based on the following assumptions:

- For inflammatory lesions: vehicle mean change = -7.6, SB204 mean change = -14.1, and a common standard deviation = 17.1
- For non-inflammatory lesions: vehicle mean change = -5.8, SB204 mean change = -11.3, and common standard deviation = 11.8

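### The secondary step-down starts without requiring success on the three co-primaries, so its error control stops at the secondary family

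*Protocol*

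**What the plan says.** Section 7.1 sets the general level: "Statistical significance will be based on two-tailed tests of the null hypothesis resulting in p-values of" 0.05 or less.

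Section 7.4.1 gives the co-primary rule: "All three co-primary outcomes must show superiority over vehicle" at that level "in order for efficacy to be demonstrated; therefore no multiplicity adjustments will be made to the co-primary outcome analyses".

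Section 7.4.2 and the synopsis give the secondary rule: "Analysis of the secondary efficacy outcomes will be adjusted for multiplicity using a hierarchical step-down procedure". The stopping trigger is internal to the secondaries: "These endpoints will be tested in the specified order with the rule that once a p-value exceeds 0.05", nothing further down counts as significant. Section 7.4.2 numbers the order:

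1. percent change in inflammatory lesions
2. percent change in non-inflammatory lesions
3. time to a 35% reduction in inflammatory lesions
4. time to a two-grade IGA improvement (listed in Section 3.1.1 as "The median time to a two (2) or more grade improvement in IGA")

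No sentence in these sections makes testing of secondary 1 depend on the co-primary results. Section 7.1 leaves detailed methodology to the SAP.

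**The concern.** A fixed sequence protects the error rate only over the hypotheses inside it. Here it begins at secondary 1, so the co-primaries and the secondaries are two separate families, each tested at 0.05. Section 7.4.1 withholds the efficacy conclusion when a co-primary fails, but it does not stop the secondary chain.

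The likely way to reach that state is visible in Section 7.8. The lesion co-primaries have large power and IGA success is the weakest of the three. If lesions succeed and IGA misses, secondaries 1 and 2 would very probably pass, assuming percent change is about as sensitive as absolute change. The protocol would then call them significant and multiplicity-adjusted in a trial where, by its own rule, efficacy was not demonstrated. What is at stake is the standing of the secondary claims, not the primary conclusion.

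**Working it through.** **1. Reproducing the plan's own figures (Section 7.8).** Inputs: IGA success 7% versus 13%; lesion differences 14.1 − 7.6 = 6.5 (SD 17.1) and 11.3 − 5.8 = 5.5 (SD 11.8); two-sided 0.05.

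- IGA sample size by the usual two-proportion formula, without continuity correction: n per arm = [1.960·√(2·0.10·0.90) + 1.645·√(0.07·0.93 + 0.13·0.87)]² / 0.06² = 646.8. That is 647 per arm, or 1294 in total, matching the stated total.
- Lesion power at 256 per arm: 99.0% (inflammatory) and 99.95% (non-inflammatory), as stated.

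**2. Which co-primary would fail.** At 647 per arm the expected z is difference / (SD·√(2/647)):

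- inflammatory: 6.5 / (17.1·√(2/647)) = 6.84
- non-inflammatory: 5.5 / (11.8·√(2/647)) = 8.38
- chance that either misses: below 0.00001

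For IGA, exact binomial power of the continuity-corrected chi-square test named in Section 7.8, at 647 per arm:

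| True rates | Power | Chance that IGA misses |
|---|---|---|
| 7% vs 13% (planned) | 94.3% | about 6% |
| 7% vs 11% (assumed) | 68.0% | about 32% |
| 7% vs 10% (assumed) | 45.2% | about 55% |

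The plan's stated power of at least 95% would put the first miss rate at 5% or less. These are frequencies of reaching the ungated state. In every row IGA has a real effect, so a miss is a type II error and not a false claim.

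**3. False claims without the gate.** Take one null co-primary and its null related secondary, with all other effects real, so that the co-primary rule turns on the null co-primary and the chain reaches the null secondary almost surely. For standard normal z-statistics with correlation ρ:

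P(false claim for SB204) = 0.025 + 0.025 − P(both z > 1.96; ρ)

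| Assumed ρ | P(both) | False claim for SB204 |
|---|---|---|
| 0.99 | 2.17% | 2.83% |
| 0.95 | 1.77% | 3.23% |
| 0.90 | 1.48% | 3.52% |
| 0.70 | 0.83% | 4.17% |

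The ceiling is 0.025 + 0.025 = 5%. The protocol gives no correlation, so the range is an assumption. When IGA is the null co-primary, the secondary concerned is number 4, the last in the order.

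**4. Simulation.** Three co-primaries and four ordered secondaries, 2,000,000 trials per scenario, correlation between domains 0.3 or 0.5. Where effects are real, mean z is 6.85 and 8.4 for the lesion endpoints (Section 7.8 effects at about 650 per arm) and 6 for IGA (assumed). False claims for SB204:

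| Scenario | No gate | Gate: all three co-primaries favour SB204 |
|---|---|---|
| One domain null, ρ from 0.99 to 0.7 | 2.80% to 4.18% | 2.47% to 2.52% |
| Global null | 2.49% to 2.58% | 0.04% to 0.16% |

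**5. A detail in the chain itself.** The stopping rule looks only at the size of p, so the chain also continues after a significant result favouring vehicle. With effective co-primaries and four independent null secondaries, false claims for SB204 are about 2.6% even with the gate. Requiring each step to favour SB204 brings this back to 2.5%.

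**The case against.** The strongest reply is that the gate is the kind of detail an SAP supplies. Section 7.1 defers methodology to the SAP, the amendment moved analysis specifics there, and a gate would add to Section 7.4.2 without contradicting it. This stands in part: it cannot be said that the trial has no gate. But the amendment removed the models and kept the step-down, so the protocol itself fixes the order, threshold and stopping trigger. That rule, read on its own, permits the secondary claims.

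Second, nothing is misstated. The protocol promises adjustment among the secondaries, and control within those four is sound. This too stands, and it limits the point to the missing link between families.

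Third, the excess is small. In the case of real lesion effects and null IGA it concerns only the last-ranked secondary. For a subject with baseline IGA 3, a two-grade improvement means a score of 0 or 1, the same threshold as IGA success, which argues for a high correlation. The two differ in timing and for subjects with baseline IGA 4, so a lower value cannot be excluded.

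A reader might also infer more than the documents support:

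- **That overall error approaches 10%.** That needs results favouring vehicle to be counted as false claims and the null co-primary to be independent of its related secondary. Two independent two-sided tests give 1 − 0.95² = 9.75%. It does not describe false claims for SB204.
- **That 32% or 55% of trials would yield false secondary claims.** Those are type II misses on IGA at assumed rates, with real effects throughout.
- **That the efficacy conclusion is compromised.** Section 7.4.1 still requires all three co-primaries.

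**Conclusion.** The point holds in limited form. As the protocol is written, error is controlled within the secondary family only, and secondaries can be labelled multiplicity-adjusted and significant after efficacy has not been demonstrated. That mislabelling follows from the text whatever the correlation. The excess in false claims for SB204 is about 0.3 to 1.7 percentage points above 2.5%. It arises under partial nulls and depends on assumed correlations of 0.99 to 0.7; under the global null it is negligible. The state would be reached mainly through an IGA miss, in about 6% of trials at the planned rates. The primary conclusion and its error rate are untouched. The sentence should be added, and the remaining uncertainty is whether the SAP already contains it.

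**What to change.** Add to Section 7.4.2 and the synopsis, and align the SAP before database lock:

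> *The secondary hierarchy is entered only if all three co-primary endpoints show superiority of SB204 at two-sided p≤0.05, and proceeds to the next endpoint only if the preceding one favours SB204 at two-sided p≤0.05; otherwise the remaining secondary p-values are descriptive.*

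If the SAP already has such a gate, the protocol text should be brought into line with it. Sample size, co-primary power and the order of the secondaries do not change. The cost is that no formal secondary claim can be made if a co-primary fails.
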